#### *Renal events*

For the EOSI renal events where selected events are adjudicated, the number (%) of patients with any renal events identified in [Table 3](#) in [Section 2.1.4.2](#) will be summarized by treatment group.

The following renal events will be listed along with the adjudication outcome if applicable, including events,

- i. recorded in e-CRF “GFR decrease”,
- ii. recorded in e-CRF “Renal Event – Dialysis”,
- iii. identified as “Renal transplant” in e-CRF “Other procedure”,

Renal death will be part of all deaths specified above.

#### *Other EOSIs*

For EOSIs that are not adjudicated, the number (%) of patients with at least one event will be summarized by treatment group and by PT (as identified in [Table 3](#) in [Section 2.1.4.2](#)).

Severe hypoglycemia will be included in the summary of hypoglycemia (See [Section 2.5.1](#)).

AE leading to an amputation is described in the section below.

#### **Analysis of Amputation**

The number (%) of patients with amputation will be summarized by treatment group and by PT and LLT during the study (ie, regardless of on- or post-treatment). Amputation is a procedure recorded in e-CRF “Other Procedures related to Amputation”. Patients who had a procedure related to amputation will be listed.

The number (%) of patients with an “AE leading to an amputation” will be summarized by treatment group and by PT. The “AE leading to an amputation” is determined by the AE identifier recorded in e-CRF “Other Procedures related to Amputation” when “AE correction” is chosen as the reason for the amputation procedure.

In addition, the number (%) of patients with an “AE potentially leading to an amputation” will be summarized by treatment group and by PT (as identified in [Table 3](#) in [Section 2.1.4.2](#); these PTs in [Table 3](#) were requested by the European Medicines Agency/ Pharmacovigilance Risk Assessment Committee[EMA/PRAC] Assessment Report 9 February 2017). Associated list will be provided as well, with patients who had an amputation procedure flagged. “AE potentially leading to an amputation” represents the condition that may potentially lead to the amputation procedure, but not in all cases an amputation has occurred (as per the EMA/PRAC request).

### **Analysis of pretreatment and posttreatment AEs**

- All pretreatment AEs by primary SOC and PT, showing the number (%) of patients with at least 1 pretreatment AE, sorted by the internationally agreed SOC order and decreasing incidence of PTs within each SOC in the sotagliflozin 400mg group.
- All posttreatment AEs by primary SOC and PT, showing the number (%) of patients with at least 1 posttreatment AE, sorted by the internationally agreed SOC order and decreasing incidence of PTs within each SOC in the sotagliflozin 400mg group.

### **Listings**

Supportive AE listings will be provided for all AEs, SAEs, and death, AEs leading to treatment discontinuation and/or death, and EOSI as appropriate. Listing of all AEs, SAEs and AEs leading to treatment discontinuation and/or death will include at least the following information, sorted by treatment, patient identification, and onset date: treatment, patient identification, country, age, gender, race, BMI, primary SOC, PT, reported term, onset date, study day (relative day to the start date of double-blind treatment), AE duration, duration of exposure, intensity, corrective treatment, action taken with IMP, date of treatment discontinuation (if relevant), relationship to IMP or NIMP, outcome, date of death (if any), seriousness, seriousness criteria, and AE status (“E” for a TEAE; and “P” for an on-study post-treatment AE).

#### **2.4.5.3 Deaths**

The following summaries of deaths will be generated.

- Number (%) of patients who died by study period (on-study, on-treatment, post-study).
- Deaths in nonrandomized patients or randomized but not treated patients.
- TEAEs leading to death (death as an outcome on the AE e-CRF page as reported by the Investigator) by primary SOC, HLGT, HLT, and PT showing number (%) of patients sorted by internationally agreed SOC order, with HLGT, HLT, and PT presented in alphabetical order within each SOC.

#### **2.4.5.4 Analyses of laboratory variables**

Laboratory parameters will be grouped and summarized by biological function as described in [Section 2.1.4.4](#).

The summary statistics (including number, mean, median, Q1, Q3, standard deviation, minimum and maximum) of all laboratory variables (central laboratory values and changes from baseline) will be calculated for each applicable visit or study assessment (screening, baseline, each postbaseline time point, last on-treatment value) by treatment group.

The incidence of PCSAs (list provided in [Appendix A](#)) at any time during the TEAE period will be summarized for each laboratory test by biological function and treatment group whatever the baseline level and/or according to the following baseline status categories:

- Normal/missing.

- Abnormal according to PCSA criterion or criteria.

For parameters for which no PCSA criteria are defined, similar table(s) using the normal range will be provided.

All measurements collected during the TEAE period, including values from unscheduled visits, will be considered for the PCSA summaries. These summaries will include patients in the safety population who have at least 1 assessment performed during the TEAE period. When a PCSA definition involves a change from baseline value, patients must also have a baseline value to be included in the summaries, and when required by the definition of the abnormality, patients must also have available laboratory normal ranges.

A listing of patients with at least 1 post-baseline PCSA (or out of normal range when no PCSA criterion is defined) will be provided and will display the entire patients' profile across time for all parameters belonging to the corresponding biological function. Individual data listings will include the following flags when applicable:

- Baseline values will be flagged "B".
- Normal laboratory ranges, available for most laboratory parameters, will be identified as ULN and LLN. Baseline, last on-treatment value, and individual data will be flagged "L" if the value is below the LLN and will be flagged "H" if it is above the ULN.
- Laboratory PCSA criteria will be used for the corresponding laboratory parameters. Values reaching a PCSA limit will be flagged (+, ++, -, or -- depending upon the direction and level of the abnormality). Flags for WBC and differential counts will be determined using data expressed in international units.

For parameters whose PCSA criteria are multiples of the ULN, the parameter's value will also be expressed as a multiple of the ULN in the individual data provided.

### **Drug-induced liver injury**

The liver function tests, namely AST, ALT, ALP, and total bilirubin, are used to assess possible drug-induced liver toxicity. The proportion of patients with PCSA values at any postbaseline visit by baseline status will be displayed by treatment group for each parameter. The proportion of patients with PCSA values at any postbaseline visit will also be displayed by duration of exposure for each treatment group (only if a tabulation summary is necessary).

Listing of possible Hy's law cases identified by treatment group (eg, patients with any elevated  $ALT > 3 \times ULN$ , and associated with an increase in bilirubin  $\geq 2 \times ULN$ ) with ALT, AST, ALP, total bilirubin, and the following complementary parameters (if available): conjugated bilirubin and prothrombin time/international normalized ratio, creatine phosphokinase, serum creatinine, complete blood count, anti-HAV IgM, anti-HBc IgM, anti-HCV and HCV RNA, anti-CMV IgM and anti-HEV IgM antibodies, auto-antibodies: anti-nuclear, anti-DNA, anti-smooth muscle, Epstein-Barr virus, herpes viruses, and anti-LKM.

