7.2.3 Exclusion criteria related to the current knowledge of sotagliflozin

- E 26. Pregnant (confirmed by serum pregnancy test at Screening) or breast-feeding women
- E 27. Women of childbearing potential not protected by highly effective method(s) of birth control and/or who are unwilling or unable to be tested for pregnancy (see [Appendix A](#))
- E 28. Mean BP after 3 separate measurements >180 mmHg (SBP) or >100 mmHg (diastolic blood pressure [DBP])
- E 29. History of hypertensive urgency or emergency within 12 weeks prior to randomization unless patient is being aggressively treated for hypertension according to local guidelines. Examples of guidelines current at the time of protocol writing include those from the ADA (10) and the European Society of Cardiology (11)
- E 30. History of gastric surgery including history of gastric banding or inflammatory bowel disease within 3 years before the Screening Visit
- E 31. Difficulty swallowing such that the patient cannot take the IMP
- E 32. Known allergies, hypersensitivity, or intolerance to sotagliflozin or any inactive component of sotagliflozin or placebo (ie, microcrystalline cellulose, croscarmellose sodium [disintegrant], talc, silicone dioxide, and magnesium stearate [nonbovine]), unless the reaction is deemed irrelevant to the study by the Investigator
- E 33. Intolerance to any SGLT2 inhibitor

- E 34. Laboratory findings with the central laboratory tests at Visit 1:
- Alanine aminotransferase (ALT) or aspartate aminotransferase (AST) $>3 \times$ the upper limit of the normal laboratory range (ULN)
 - Total bilirubin $>1.5 \times$ ULN (except in case of Gilbert's syndrome)
 - Neutrophils $<1,500/\text{mm}^3$ (or according to ethnic group; see [Appendix D](#) for details) and/or platelets $<100,000/\text{mm}^3$
 - Amylase and/or lipase $>3 \times$ ULN
 - Fasting triglycerides $>600 \text{ mg/dL}$ ($>6.77 \text{ mmol/L}$) unless value determined to be due to nonfasting status in which case it may be repeated once
- E 35. Severe renal disease as defined by eGFR of $<30 \text{ mL/min/1.73m}^2$ at screening by the 4 variable Modification of Diet in Renal Disease equation
- E 36. Renal disease that required treatment with immunosuppressive therapy or a history of dialysis or renal transplant or initiation of chronic dialysis within 4 weeks prior to the Screening Visit or expected to occur within 180 days after the Screening Visit

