**for phase 2/3 studies (oncology excepted)**  
**(From BTD-009536 May 21, 2014)**

Parameter	PCSA	Comments
Clinical Chemistry		
ALT	By distribution analysis : >3 ULN >5 ULN >10 ULN >20 ULN	Enzymes activities must be expressed in ULN, not in IU/L. Concept paper on DILI – FDA draft Guidance Oct 2007. Internal DILI WG Oct 2008. Categories are cumulative. First row is mandatory. Rows following one mentioning zero can be deleted.
AST	By distribution analysis : >3 ULN >5 ULN >10 ULN >20 ULN	Enzymes activities must be expressed in ULN, not in IU/L. Concept paper on DILI – FDA draft Guidance Oct 2007. Internal DILI WG Oct 2008. Categories are cumulative. First row is mandatory. Rows following one mentioning zero can be deleted.
Alkaline Phosphatase	>1.5 ULN	Enzymes activities must be expressed in ULN, not in IU/L. Concept paper on DILI – FDA draft Guidance Oct 2007. Internal DILI WG Oct 2008.
Total Bilirubin	>1.5 ULN >2 ULN	Must be expressed in ULN, not in µmol/L or mg/L. Categories are cumulative. Concept paper on DILI – FDA draft Guidance Oct 2007. Internal DILI WG Oct 2008.
Conjugated Bilirubin	>35% Total Bilirubin and TBILI>1.5 ULN	Conjugated bilirubin dosed on a case-by-case basis.
ALT and Total Bilirubin	ALT>3 ULN and TBILI>2 ULN	Concept paper on DILI – FDA draft Guidance Oct 2007. Internal DILI WG Oct 2008. To be counted within a same treatment phase, whatever the interval between measurement.
CPK	>3 ULN	FDA Feb 2005.

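### The SAP's combined transaminase-bilirubin screen is triggered by ALT alone, so an AST-led case gets no possible Hy's law flag and no by-arm count

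*SAP*

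**What the plan says.** SAP 2.4.5.4, under drug-induced liver injury, gives the tests it relies on: "namely AST, ALT, ALP, and total bilirubin, are used to assess possible drug-induced liver toxicity". It then plans a "Listing of possible Hy's law cases identified by treatment group (eg, patients with any elevated" ALT above 3 x ULN, "and associated with an increase in bilirubin" to at least 2 x ULN. For each listed patient it shows AST, ALP and total bilirubin beside ALT, with complementary results where available, including CPK, coagulation, viral serology and autoantibodies.

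Appendix A defines the potentially clinically significant abnormalities (PCSAs) that are tabulated by arm. ALT and AST have identical grades, "By distribution analysis : >3 ULN >5 ULN >10 ULN >20 ULN", and total bilirubin has ">1.5 ULN >2 ULN". There is one row that combines a transaminase with bilirubin: "ALT>3 ULN and TBILI>2 ULN". Its timing note reads "To be counted within a same treatment phase, whatever the interval between measurement".

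In the protocol, the example of a medically important event in 10.4.1.2 also pairs ALT above 3 x ULN with total bilirubin above 2 x ULN. Exclusion criterion E 34 (7.2.3) applies the limit of 3 x ULN to ALT or AST.

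**The concern.** The plan measures both transaminases, grades them identically and treats them alike at entry. In the two places where the analysis looks for a transaminase rise together with raised bilirubin, however, AST cannot trigger the flag. It is displayed only after ALT has qualified the patient.

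The combined pattern is the part of the liver-safety analysis that readers will look for first. The documents give no expected frequency. If there are few or no such cases in about 500 patients (an assumption), one unflagged case would change how the summary reads.

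There is also a smaller inconsistency. The listing and the Appendix A row use different bilirubin inequalities, and only Appendix A states a timing rule. A programmer therefore has two definitions of what should be the same event.

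**Working it through.** The plan states no figure here to reproduce. The check is to apply the rules to hypothetical patients, with all values in multiples of ULN and TB meaning total bilirubin.

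Rules:
- Listing (SAP 2.4.5.4): ALT > 3 and TB >= 2.
- Combined row (SAP Appendix A): ALT > 3 and TB > 2.
- Proposed: (ALT > 3 or AST > 3) and TB >= 2.
- Single-test PCSAs (Appendix A): AST > 3; TB > 1.5 and TB > 2.

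| ALT | AST | TB | Listing | Combined row | Proposed | AST > 3 | TB > 2 |
|---|---|---|---|---|---|---|---|
| 4 | 2 | 2.5 | yes | yes | yes | no | yes |
| 4 | 2 | 2.0 | yes | no | yes | no | no |
| 3 | 5 | 2.5 | no | no | yes | yes | yes |
| 2 | 5 | 2.5 | no | no | yes | yes | yes |
| 2 | 5 | 2.0 | no | no | yes | yes | no |
| 2 | 5 | 1.8 | no | no | no | yes | no |

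Three results follow.

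1. **AST gap.** Any patient with AST > 3, ALT <= 3 and TB >= 2 fails both current rules. The patients with (ALT, AST, TB) of (3, 5, 2.5) and (2, 5, 2.5) meet the AST and bilirubin PCSAs separately but no combined criterion.

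2. **Bilirubin cut-off.** The listing and the combined row disagree only when TB is exactly 2.0, as in the second case: listed but not counted. Aligning both at > 2 would remove that patient from the listing. Aligning both at >= 2 removes no one.

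3. **Where an AST-led patient still appears.** For (2, 5, 2.5), SAP 2.4.5.4 counts the AST and bilirubin abnormalities by arm in separate tables. Its general PCSA listing then shows the patient's values over time for every test in the same biological function, with PCSA values flagged. SAP 2.1.4.4 puts ALT, AST, ALP and total bilirubin in one function (liver), so they are seen together. Three things are missing: the possible Hy's law label, a by-arm count of the combination, and the complementary results specified for the Hy's law listing. CPK is grouped under metabolism in 2.1.4.4, so the liver profile does not bring it in.

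**The case against.** The strongest reply is that nothing is lost. The general PCSA listing shows an AST-led patient with all four liver tests over time, flagged and expressed as multiples of ULN. That is correct. A reader might infer from the ALT-only rule that such a patient goes unidentified altogether, and the documents do not support this. What is missing is the combined flag, the combined count and the specified complementary results.

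Second, the listing rule is introduced as an example, so it does not bar an AST-led case. This also stands, but no other criterion is given, and the Appendix A row is not worded as an example.

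Third, ALT is a consistent trigger across the plan: the medically important event example, the adverse event of special interest, the laboratory-management list and SAP Table 3 all use it. E 34 is a screening criterion with a different purpose and a bilirubin limit of 1.5 x ULN. That is fair. E 34 shows that the plan regards AST above 3 x ULN as notable, not that the post-baseline screen must include it. The change is an improvement rather than the repair of a contradiction.

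Fourth, a blinded committee reviews potential drug-induced liver injury (Protocol 6.4.4). Its charter is not among the documents, so they show neither that it would catch an AST-led case nor that it would miss one. A claim that the programme would overlook such a case is therefore unsupported.

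**Conclusion.** The point holds in a limited form. Under the stated criteria, a patient with AST above 3 x ULN, ALT at or below 3 x ULN and bilirubin above the limit is neither flagged nor counted by arm as a possible Hy's law case, although the underlying values are tabulated and listed.

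It is a cheap improvement to safety reporting. It touches no efficacy result, error rate or power figure. How often it would matter cannot be estimated from the documents, because no rate of AST-led combined elevations is given.

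The bilirubin mismatch is minor. A reader might infer that the listing and the table could differ materially on it, but they part only at exactly 2.0 x ULN, where the listing is the wider of the two. The missing timing rule in 2.4.5.4 is a similar small ambiguity that the same edit can settle.

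**What to change.** In SAP 2.4.5.4 and in Appendix A, state one analysis criterion: ALT or AST above 3 x ULN, with total bilirubin at or above 2 x ULN. If the sponsor's standard PCSA set has to stay as issued, add the criterion to Appendix A as a study-specific row.

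- Use it for both the listing and the by-arm count, and show whether ALT, AST or both qualified.
- Keep the wider bilirubin limit of 2.4.5.4, so that no patient who would be listed now is dropped.
- State one timing rule in both places. The Appendix A rule (same treatment phase, any interval) is already written and could be carried over.

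The cost is one added OR condition in the program and a line of wording in each place. AST is in the same chemistry panel as ALT (Protocol Table 2), so no extra sample is needed. The downside is that an AST rise of muscle origin will occasionally be listed; the CPK result already planned for that listing helps to separate these.

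This alters analysis flagging only. The protocol's reporting and management rules stay as they are. The SAP should say that its analysis criterion is deliberately wider than the ALT-based example in Protocol 10.4.1.2.

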#### **2.4.5.5 Analyses of vital sign variables**

The summary statistics (including number, mean, median, Q1, Q3, standard deviation, minimum and maximum) of heart rate, temperature and respiratory rate (observed values or mean of observed values, and changes from baseline) will be calculated for each applicable visit or study assessment (baseline, post-baseline time points, last on-treatment value) by treatment group.

The incidence of PCSAs at any time during the TEAE period will be summarized by treatment group for SBP, DBP and HR. All measurements collected during the TEAE period, including values from unscheduled visits, will be considered for the PCSA summaries. The summaries will include patients in the safety population who have at least 1 assessment performed during the TEAE period. When a PCSA definition involves a change from baseline value, patients must also have a baseline value to be included in the summaries.

A listing of patients with at least 1 post-baseline PCSA will be provided and will display the patient's profile over time of all vital sign parameters. Individual data listings will include the following flags:

- Baseline values will be flagged "B".
- Parameter values reaching a PCSA limit will be flagged (+, or - depending of the direction).

#### **2.4.5.6 Analyses of electrocardiogram variables**

Shift tables will be provided to present ECG status according to baseline status (Normal/Missing, Abnormal) for each treatment group during the TEAE period. Supportive listings of patients with abnormal ECG status at any post-baseline visit will be provided.

#### **2.4.5.7 Analyses of physical examination variables**

Shift tables will be provided to present physical examination findings by body system according to baseline status (Normal/Missing, Abnormal) for each treatment group during the TEAE period. Supportive listings of patients with abnormal findings at any post-baseline visit will be provided.

#### **2.4.6 Analyses of pharmacokinetic variables**

Plasma concentrations of sotagliflozin and its 3-O-glucuronide metabolite will be summarized by visit and nominal sampling time (pre-dose at Weeks 4, 18, 26, 52, and 79, and 1 hour 30 minutes post-dose at Week 26 and 79) in the PK population (see [Section 2.3.3](#)) in the sotagliflozin 400 mg group, using descriptive statistics such as number, geometric mean, coefficient of variation, median, minimum and maximum. Individual plasma concentrations of sotagliflozin and its 3-O-glucuronide metabolite at nominal sampling times will also be listed.

## 2.5 DATA HANDLING CONVENTIONS

### 2.5.1 General conventions

The following formulas will be used for computation of parameters.

#### *HbA1c*

The formula to convert HbA1c from Diabetes Control and Complications Trial (DCCT) aligned value to International Federation of Clinical Chemistry and Laboratory Medicine (IFCC) standardized value is,

$$\text{IFCC-HbA1c (mmol/mol)} = [\text{DCCT-HbA1c (\%)} - 2.15] \times 10.929.$$

#### *Renal function formulas*

The estimated GFR (mL/min/1.73 m^2) will be calculated using the 4 variable Modification of Diet in Renal Disease (MDRD) formula:

$$\text{Standard unit: eGFR (mL/min/1.73 m}^2\text{)} = 175 \times [\text{Serum Creatinine } (\mu\text{mol/L})/88.4]^{-1.154} \times \text{Age (year)}^{-0.203} \times 1.212 \text{ (if Black)} \times 0.742 \text{ (if female)}.$$

$$\text{Conventional unit: eGFR (mL/min/1.73 m}^2\text{)} = 175 \times \text{Serum Creatinine (mg/dL)}^{-1.154} \times \text{Age (year)}^{-0.203} \times 1.212 \text{ (if Black)} \times 0.742 \text{ (if Female)}.$$

#### *Calculation of LDL-C*

When TG is lower than or equal to 4.52 mmol/L (400 mg/dL), LDL-C is calculated using the Friedewald equation as:

- In standard unit (mmol/L),  $\text{TC} - \text{HDL-C} - \text{TG}/2.17$ .
- In conventional unit (mg/dL),  $\text{TC} - \text{HDL-C} - \text{TG}/5$ .

### 2.5.2 Data handling conventions for secondary efficacy variables

Scheduled measurements (see [Section 2.5.4](#)) of continuous efficacy variables collected during the study will be used in the analyses including those obtained after IMP discontinuation or introduction of rescue therapy. Continuous secondary efficacy endpoints will be analyzed with missing values imputed by retrieved dropouts MI method or by the washout MI method according to the criterion described in [Section 2.4.4.1](#).

For the categorical secondary efficacy endpoints, data handling conventions are described in [Section 2.4.4.2](#).

### 2.5.3 Missing data

For categorical variables, patients with missing data are not included in calculations of percentages unless otherwise specified. When relevant, the number of patients with missing data

is presented.

Derived variables will be considered missing if any of the original variables required to calculate them are missing. For example, if either a baseline assessment or an endpoint assessment is missing for a particular patient, then change from baseline at endpoint will be missing. Depending upon the assessment, analyses may not include all patients in the analysis population, because certain patients in the intended population may have missing data.

